Study Design: 
This Phase 2, randomized, double-blind, multi-center study will evaluate the efficacy, safety, and pharmacokinetics (PK) of etrasimod compared with placebo in adults with active EoE. The study will consist of a Screening Period of up to 35 days, 24 weeks of double-blind treatment (Double-Blind Treatment Period), 28 weeks of active extended treatment (Extension Treatment Period), and 4 weeks of follow-up (Safety Follow-Up Period) for a total study duration of up to 61 weeks.
 
Eligible subjects will be randomized in a double-blind fashion (3:3:2 ratio) to etrasimod 1 mg, etrasimod 2 mg, or matching placebo once daily. Randomization will be stratified by baseline history of esophageal dilation (yes/no) and concurrent proton pump inhibitor (PPI) therapy (yes/no).
 
All subjects who complete the Double-Blind Treatment Period and meet eligibility criteria for the Extension Treatment Period may enter the Extension Treatment Period. Subjects who were in the etrasimod 1 mg or etrasimod 2 mg groups in the Double-Blind Treatment Period will continue the same etrasimod dose in the Extension Treatment Period. Subjects who were in the placebo group during the Double-Blind Treatment Period will be re-randomized (1:1 ratio) to etrasimod 1 mg or etrasimod 2 mg at entry into the Extension Treatment Period.
 
Subjects will have follow-up visits at 2 and 4 weeks after the last dose of study treatment after Week 52 or the Early Termination (ET) Visit.

Number of Subjects (planned):

Approximately 96 subjects are planned to be enrolled.

Eligibility Criteria for the Double-Blind Treatment Period:

Key Inclusion Criteria (Full Inclusion Criteria Are Provided in the Protocol)

- Men or women between 18 and 65 years of age at the time of informed consent (IC)
- Have an EoE diagnosis prior to screening and histologically active disease with an esophageal peak eosinophil count (PEC) of ≥ 15 eosinophils (eos)/high power field (hpf) (~ 60 eos/mm²) from any level (proximal, mid, or distal) of the esophagus at the Screening esophagogastroduodenoscopy (EGD)
- Have dysphagia, defined as solid food going down slowly or getting stuck in the throat with an average frequency of ≥ 2 episodes per week over 2 weeks (as documented using the Dysphagia Symptom Questionnaire (DSQ) during the Screening period)

Key Exclusion Criteria (Full Exclusion Criteria Are Provided in the Protocol)

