Proportion-based secondary endpoints (eg, histologic responders or symptomatic responders) at Week 16 will be analyzed in the FAS; subjects who use rescue medication or have a rescue procedure, or with missing data for any reason will be considered a "non-responder" or "failure." The analyses will be performed using the Cochran-Mantel-Haenszel (CMH) method adjusted for randomization stratification factors. The number and percentage of subjects achieving the goal and the difference in proportion between treatment groups achieving the goal, along with p-value and the 95% CIs will be reported.

Longitudinal continuous endpoints (Section 11.5.1.2) will also be analyzed up to Week 24 using a linear mixed effects model. The model will include treatment group, visit, interaction of treatment-by-visit, and randomization stratification factors as factors, and Baseline measure as covariates. An unstructured covariance matrix will be specified for the within-subject measurements. LS means and LS mean differences between treatment group with unadjusted p-values and corresponding 95% CIs will be reported at each scheduled visit. This method will also be applied to other score based or continuous measures.

CCI

Endpoints measured during the Extension Treatment Period after Week 24 up to Week 52 will be summarized using descriptive statistics without inferential comparison. Dichotomous remission or response outcomes derived from specific scores will be assessed. Continuous variables will be summarized by visit using the number of observations, mean, SD, median, minimum, and maximum; and categorical variables will be summarized by visit using frequency counts and percentages, with following considerations:

- Four treatment sequence (as listed below) in the Extension Treatment Period will be analyzed, if applicable
 - etrasimod 1 mg-1 mg
 - etrasimod 2 mg-2 mg
 - placebo - etrasimod 1 mg
 - placebo - etrasimod 2 mg
- Change from baseline in continuous variables will be analyzed on change from Baseline in the Double-Blind Treatment Period and change from Baseline in the Extension Treatment Period

CCI

In addition to between group analyses on the primary and secondary endpoints, dose-response relationship will be investigated using exposure-response modeling and the details will be described in the PK/PD analysis document. The PK/PD modeling will be written as a standalone document.

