6.4. WINDOWING CONVENTIONS

All scheduled study visits are defined relative to Study Day 1, the date of first dose. Scheduled visit windows are defined in Appendix 1 of the protocol. A windowing convention will be used to determine the analysis visit value for a given measurement and will be applicable for all by-visit summaries and analyses for efficacy and safety data. See Table 3 below for specific visit windows.

Visit Windows for Efficacy and Safety Analyses

For all efficacy (except for DSQ total score), CCI health-related quality of life, safety labs and vital signs.	
Scheduled Study Visit (Protocol Scheduled Day)	Analysis Visit Window (Study Day)
Baseline (Double-Blind Treatment Period)	≤ 1 , in addition to Study Day ≤ 1 , a measurement also needs to fulfill the baseline criteria identified in Section 6.2 in order to be considered as baseline measurement
Week 0 (Day 1)	1
Week 2 (Day 15 \pm 3)	2 to 22
Week 4 (Day 29 \pm 3)	23 to 43
Week 8 (Day 57 \pm 5)	44 to 71
Week 12 (Day 85 \pm 5)	72 to 99
Week 16 (Day 113 \pm 5)	100 to 127
Week 20 (Day 141 \pm 5)	128 to 155
Week 24 (Day 169 \pm 5)	156 to 183
Week 28 (Day 197 \pm 7)	184 to 211
Week 32 (Day 225 \pm 7)	212 to 274
Week 46 (Day 323 \pm 7)	275 to 344
Week 52 (Day 365 \pm 7)	> 344

DSQ total score will be calculated every 2 weeks (week 0, 2, 4, 6, 8, 10, etc.) based on the scheduled study day starting on Day 1 For example, DSQ total score for Week 2, 4 and 6 will be calculated on Day 15, 29 and 43, respectively. .

For ECGs, OCT, and PFT.

Scheduled Study Visit (Protocol Scheduled Day)	Analysis Visit Window (Study Day)
Baseline (Double-Blind Treatment Period)	≤ 1
Week 0 (Day 1)	1
Week 24 (Day 169 ± 5)	71 to 267
Week 52 (Day 365 ± 7)	> 267

Windowing will be applied prior to any missing data calculations. The measurement that meets the Baseline criteria described in Section 6.2 will be labeled as “Baseline”. Unscheduled or Screening visits that occurred before the Baseline visit will not be assigned an analysis visit. The early discontinuation visit will be eligible for allocation to an analysis visit. The 2- and 4-Week Follow-Up visits will not be included in the visit windows and will be summarized separately without any window applied.

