^b No missing data methods will be implemented since missing data will be handled in the linear mixed effect model.

^c Subjects who initiate rescue medication/rescue procedure will have assessments collected after the rescue medication/rescue procedure is initiated set to missing.

^d Subjects who initiate rescue medication/rescue procedure will have assessments collected after the rescue medication/rescue procedure is initiated set to missing. Missing data for any reason will be considered as nonresponder. Adjusted difference and p-values are based on the estimated common risk difference using the MH weights

^e Subjects who initiate rescue medication/rescue procedure will have assessments collected after the rescue medication is initiated set to missing. Missing data will be imputed using multiple imputation.

^f primary approach (14-day period approach) will be used to calculate DSQ total score

^g sensitivity approaches (14-day period: worst case scenario approach and 7-day period approach) will be used to calculate DSQ total score.

In addition, some of the additional analyses above will be conducted as follows:

Percent change from baseline in esophageal PEC at Week 16 above will be repeated at week 24 using the same ANCOVA model.

Change from baseline in DSQ total score at Week 16 above will be repeated for week 2, 4, 6, 8, 10, 12, 14, 20 and 24 in Double-Blind Treatment Period, using the same linear mixed effects model for change from baseline in DSQ total score at Week 16.

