17.2.3. PRIMARY ANALYSIS OF SECONDARY EFFICACY VARIABLES

17.2.3.1. Change from Baseline in DSQ total score and Esophageal PEC at Week 16

Analysis of the secondary efficacy variables change from Baseline in DSQ total score at Week 16 will use a linear mixed effect model. The linear mixed effect model will include treatment group, visit, interaction of treatment-by-visit, Baseline history of esophageal dilation (Yes or No), and concurrent PPI therapy (Yes or No) as factors and Baseline DSQ total score as a covariate using an unstructured covariance matrix. If there is a convergence issue in fitting the unstructured covariance, a compound symmetry covariance structure will be used. The Kenward-Rogers method will be used to estimate the denominator degrees of freedom. Change from Baseline in Esophageal PEC at Week 16 will use an ANCOVA model including treatment group and randomization stratification factors as factors and Baseline eosinophil PEC as a covariate. Eosinophil PEC assessments after rescue medication and/or rescue procedure use will be set to missing. LS means at visit and LS mean differences between treatment groups (i.e. etrasimod 1 mg vs placebo, etrasimod 2 mg vs placebo, and etrasimod pooled vs placebo) with p-values and corresponding 95% CIs will be reported. For the individual etrasimod summaries, treatment group will include placebo, etrasimod 1 mg and etrasimod 2 mg. For the pooled etrasimod summary, treatment group will include placebo and pooled etrasimod.

17.2.3.2. Proportion of Subjects with Esophageal PEC < 15 and ≤ 6 eos/hpf at Week 16

Analysis of the secondary efficacy variables proportion subjects with esophageal PEC < 15 eos/hpf at Week 16 and proportion of subjects with esophageal PEC ≤ 6 eos/hpf at Week 16 will be performed for randomization stratification factors of baseline history of esophageal dilation (Yes or No) and concurrent PPI therapy (Yes or No). Subjects who use rescue medication or have a rescue dilation, or with missing data at Week 16 for any reason will be considered nonresponders. The stratified analyses will be performed for randomization stratification factors. Results will be expressed as the number and percentage of subjects who achieved the goal, risk difference in

CCI [REDACTED]

- | [REDACTED]
- | [REDACTED]
- | [REDACTED]
- | [REDACTED]
- | [REDACTED]
- | [REDACTED]
- | [REDACTED]

CCI [REDACTED]

[REDACTED]

CCI [REDACTED]

CCI [REDACTED]	[REDACTED]	[REDACTED]	[REDACTED]	[REDACTED]

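### If the unstructured DSQ model does not converge, the SAP's only fallback is homogeneous compound symmetry with model-based errors, and the Week 16 standard error can then be too small or too large

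*SAP*

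**What the plan says.** SAP 17.2.3.1 analyses change from baseline in DSQ total score with a linear mixed model containing treatment, visit, their interaction, the two stratification factors and "Baseline DSQ total score as a covariate using an unstructured covariance matrix". If that fit fails there is a single alternative: "If there is a convergence issue in fitting the unstructured covariance, a compound symmetry covariance structure will be used". On inference it says "The Kenward-Rogers method will be used to estimate the denominator degrees of freedom", and it names no empirical (sandwich) standard error.

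Protocol 11.5 has the unstructured choice only ("An unstructured covariance matrix will be specified for the within-subject measurements") and gives no fallback.

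The number of visits in the model can be read in two ways. SAP 17.2.1 says the Week 16 analysis "will be repeated for week 2, 4, 6, 8, 10, 12, 14, 20 and 24 in Double-Blind Treatment Period", which with Week 16 makes 10 visits. SAP 6.4 says "DSQ total score will be calculated every 2 weeks", which gives 12 post-baseline scores to Week 24. On size, the protocol synopsis says "Approximately 96 subjects are planned to be enrolled", allocated 3:3:2.

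**The concern.** The SAP goes from the most flexible covariance to one of the most restrictive in a single step. The unstructured matrix gives each visit its own variance. Homogeneous compound symmetry forces one variance on all visits and one correlation on every pair, from adjacent visits to those 22 weeks apart. No structure in between keeps visit-specific variances.

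At stake are the Week 16 confidence intervals and p-values for 1 mg, 2 mg and pooled etrasimod against placebo on the first-listed secondary endpoint. Kenward-Roger allows for the covariance parameters being estimated, but it takes the assumed form as correct. The main DSQ model also imputes nothing (SAP 17.2.1, note b to the planned-analyses table), so the working covariance also governs how earlier scores inform missing Week 16 values.

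**Working it through.** The documents state no DSQ SD, correlation, dropout rate or effect size, so there is no figure of theirs to reproduce. Every SD pattern below is an assumption.

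**Inputs from the documents.** About 96 subjects at 3:3:2: 96 × 3/8 = 36, 36, and 96 × 2/8 = 24 on placebo. Two-sided 5% tests (SAP 6.5). Covariance parameters for k visits are k(k+1)/2: 10 × 11/2 = 55, or 12 × 13/2 = 78.

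**Closed form, complete data.** Under compound symmetry the Week 16 contrast is the difference in adjusted Week 16 means, but its variance uses the pooled value. The sample-size term (1/36 + 1/24) cancels:

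- model SE / true SE = R = √(mean of visit variances / Week 16 variance)
- actual alpha = 2 × [1 − Φ(1.96 × R)]

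Let SD change linearly from 1 at Week 2 to 1 + d at Week 24, with x = (week − 2)/22. The mean variance is then 1 + 2d·mean(x) + d²·mean(x²). For the 10 visits, mean(x) = 0.4364 and mean(x²) = 0.2826. At Week 16, x = 14/22 = 0.6364.

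Worked case, d = 0.5 (a 1.5-fold rise): mean variance = 1 + 0.4364 + 0.25 × 0.2826 = 1.507. Week 16 variance = (1 + 0.5 × 0.6364)² = 1.738. R = √(1.507/1.738) = 0.931. Alpha = 2 × [1 − Φ(1.825)] = 6.8%.

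| SD, Week 2 to Week 24 | R, 10 visits | alpha | R, 12 visits | alpha |
|---|---|---|---|---|
| rises 1.25× | 0.959 | 6.0% | 0.973 | 5.7% |
| rises 1.5× | 0.931 | 6.8% | 0.956 | 6.1% |
| rises 2× | 0.897 | 7.9% | 0.937 | 6.6% |
| falls to 0.67× | 1.091 | 3.3% | 1.065 | 3.7% |

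Two unsteady patterns, 10 visits. SD flat to Week 16 and then rising to 1.5× at Week 24 gives R = 1.087 and alpha 3.3%. SD with a hump at Week 16, equal to 1 + 0.5·exp(−((week − 16)/5)²), gives R = 0.786 and alpha 12.3%.

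**Simulation with serial correlation and dropout.** Compound symmetry was fitted by REML with 24/36/36 subjects, 10 visits, correlation 0.95 per week and 1,500 runs per row. Monte Carlo error near 5% is √(0.05 × 0.95/1500) = 0.6 points.

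| SD pattern | dropout | SE ratio, model-based | alpha | alpha, sandwich SE |
|---|---|---|---|---|
| constant | 0 | 1.005 | 5.2% | 5.1% |
| constant | 20% | 0.984 | 4.9% | 4.4% |
| rises 1.5× | 0 | 0.949 | 6.1% | 4.5% |
| rises 1.5× | 20% | 0.880 | 8.4% | 5.9% |
| rises 2× | 20% | 0.892 | 8.4% | 5.1% |
| falls to 0.67× | 20% | 1.078 | 2.7% | 4.7% |

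With constant SD, a wrong correlation form does little harm. The error comes from unequal variances, and dropout enlarged it for the 1.5-fold rise. The tests used fixed degrees of freedom (200 model-based, 90 sandwich). Kenward-Roger itself was not coded.

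**A case where variability changes and nothing goes wrong.** Let SD rise from 1.00 at Week 2 to 1.25 at Week 16 and 1.78 at Week 24. The mean variance over the 10 visits is 1.5625 = 1.25², equal to the Week 16 variance, so R = 1.000. Simulated over 3,000 runs: ratio 0.996, alpha 5.3%.

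**The case against.** The strongest objection is that the fallback may never be used. A count of 55 or 78 parameters against 96 subjects shows that non-convergence is possible, not that it is likely. The covariance is pooled over arms, so about 96 subjects inform it, not the 24 on placebo. In a separate simulation of the unstructured model (normal data, 36/36/24, 10 or 12 visits, 20% or 40% dropout, 5% intermittent missing values), all 1,300 completed fits converged. That used purpose-written code rather than SAS, well-behaved data and an incomplete 12-visit grid, so it does not exclude failure. It does mean that a reader should not infer from the documents that failure is expected.

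Second, direction. A reader might infer that the fallback overstates significance because variance tends to grow over time. The documents contain nothing on how DSQ variance behaves. The score is bounded at 0 and 84, and improvement towards the floor could shrink the variance and make the test conservative.

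Third, importance. DSQ is a secondary endpoint, p-values are unadjusted by design (Protocol 11.7, SAP 8.4), and the SAP also lists multiple-imputation, tipping-point, Completers and Per Protocol analyses for it. The text of SAP 17.2.4 and 17.2.5 does not appear in the public copy, so further handling there cannot be ruled out.

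All three limit the weight of the point. None removes it: SAP 17.2.3.1 governs the main DSQ analysis, and the supporting analyses do not replace its Week 16 standard error.

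**Conclusion.** The gap is real and conditional. If the unstructured fit fails, the stated rule gives a Week 16 standard error that can be too small or too large when the Week 16 variance differs from the average over visits. For SDs changing steadily by 1.25 to 2 times, the error is about 3 to 12% of the standard error, with actual alpha about 3% to 8%. The 12% end includes 20% dropout; a hump at Week 16 would be worse. All of these sizes rest on assumed SDs.

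A reader might infer that the standard error is wrong whenever variability changes over time. That is too strong, as the last case in the working shows: what counts is Week 16 against the visit average. The primary PEC analysis is unaffected. This is a cheap improvement to a contingency rule, not a flaw in the planned main model.

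**What to change.** Keep all scheduled DSQ visits and replace the single fallback in SAP 17.2.3.1 with a fixed order, taking the first structure that converges:

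1. heterogeneous Toeplitz (10 variances + 9 correlations = 19 parameters for 10 visits)
2. heterogeneous AR(1) (10 + 1 = 11)
3. heterogeneous compound symmetry (10 + 1 = 11)
4. homogeneous compound symmetry (2), only as a last resort

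Retain Kenward-Roger for the heterogeneous structures. If a sandwich standard error is used for any fit that is not unstructured, specify a small-sample correction and a degrees-of-freedom rule in place of Kenward-Roger.

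State whether 10 or 12 visits enter the model. With the 10-visit list the last two gaps are four weeks rather than two, and Toeplitz and AR(1) by visit order would treat them as equal. Thinning to 4-weekly visits is not a good first step, because SAP 17.2.1 requires estimates at Weeks 2, 6, 10 and 14 from the same model.

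The cost is a few lines of SAP wording and no new data. If the sandwich is used, standard errors will be slightly noisier at this sample size.

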The primary and secondary endpoints will be analyzed using the Full Analysis Set (FAS) and demographic and safety analyses will be performed using the Safety Set. Other important statistical considerations, such as handling rescue medication/rescue procedure uses during study treatment, missing data imputation strategies, sensitivity analyses, and subgroup analyses will be described in the protocol and the SAP.

The endpoints of percentage change in esophageal PEC from Baseline to Week 16 and Week 24 will be analyzed using analysis of covariance (ANCOVA) model based on rank scores due to the skewed distribution of the data and possible outliers. The ANCOVA model will include treatment group and randomization stratification factors as factors and Baseline eosinophil PEC as a covariate. PEC after rescue medication/rescue procedure uses will be set to missing; all missing data will be imputed in the FAS using multiple imputation (MI) procedure as appropriate. Multiple results of ANCOVA (least square [LS] mean rank scores and LS mean rank score difference from placebo) for each MI dataset will be analyzed and reported along with final p-value using Rubin's method [1]. In addition, a descriptive summary of percentage change in esophageal PEC from baseline as well as the difference between treatment groups will be presented by treatment group. When applying the same ANCOVA model to key secondary continuous variables, no rank transformation will be used.

Proportion-based secondary endpoints (eg, histologic responders or symptomatic responders) at Week 16 will be analyzed in the FAS; subjects who use rescue medication or have a rescue procedure, or with missing data for any reason will be considered a "nonresponder" or "failure." The analyses will be performed using the Cochran-Mantel-Haenszel (CMH) method adjusted for randomization stratification factors. The number and percentage of subjects achieving the goal and the difference in proportion between treatment groups achieving the goal, along with p-value and the 95% CIs will be reported.

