3. STUDY DESIGN

3.1. Overall Design

This Phase 2 randomized, double-blind, multi-center study will evaluate the efficacy, safety, and PK of etrasimod compared with placebo for 24 weeks in adults with active EoE.

The study will consist of a Screening Period of up to 35 days, 24 weeks of double-blind treatment (Double-Blind Treatment Period), 28 weeks of active extended treatment (Extension Treatment Period), and 4 weeks of follow-up (Safety Follow-Up Period) for a total study duration of up to 61 weeks.

Eligible subjects will be randomized in a double-blinded fashion (3:3:2 ratio) to etrasimod 1 mg, etrasimod 2 mg, or matching placebo once daily. Randomization will be stratified by baseline history of esophageal dilation (yes/no) and concurrent PPI therapy (yes/no).

[figure not shown]
All subjects who complete the Double-Blind Treatment Period and meet eligibility criteria for the Extension Treatment Period may enter the Extension Treatment Period.

Subjects who were in etrasimod 1 mg or etrasimod 2 mg groups in the Double-Blind Treatment Period will continue the same etrasimod dose in the Extension Treatment Period. Subjects who were in the placebo group during the Double-Blind Treatment Period will be re-randomized (1:1 ratio) to etrasimod 1 mg or etrasimod 2 mg at entry into the Extension Treatment Period.

Subjects will have follow-up visits at 2 and 4 weeks after the last dose of study treatment after Week 52 or the Early Termination (ET) Visit.

A study design schematic is shown in [Figure 1](#).

Figure 1: Study Design

*Esophagogastroduodenoscopy
 EoE, eosinophilic esophagitis; ETR, etrasimod; F/U, follow-up; PBO, placebo.
 Numbers preceded by colons represent the randomization ratio.

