11.5. Efficacy Analyses

For the Double-Blind Treatment Period, the primary and secondary endpoints will be analyzed using the FAS. Other important statistical considerations, such as handling rescue medication/rescue procedure uses during study treatment, missing data imputation strategies, sensitivity analyses, and subgroup analyses will be described in the SAP.

The endpoints of percentage change in esophageal PEC from Baseline to Week 16 and Week 24 will be analyzed using analysis of covariance (ANCOVA) model based on rank scores due to the skewed distribution of the data and possible outliers. The ANCOVA model will include treatment group and randomization stratification factors as factors and Baseline eosinophil PEC as a covariate. PEC after rescue medication/rescue procedure uses will be set to missing; all missing data will be imputed in the FAS using MI procedure as appropriate. Multiple results of ANCOVA (least square [LS] mean rank scores and LS mean rank score difference from placebo) for each MI dataset will be analyzed and reported along with final p-value using Rubin's method [1]. In addition, a descriptive summary of percentage change in esophageal PEC from baseline as well as the difference between treatment groups will be presented by treatment group. When applying the same ANCOVA model to key secondary continuous variables, norank transformation will be used.

For the efficacy endpoints of the percentage change in esophageal PEC from Baseline at Week 16 and Week 24, in the FAS, subjects who have experienced intercurrent events, such as rescue medication/rescue procedure use, early discontinuation of study treatment, etc., will be included in the analysis and their missing data at Week 16 and Week 24 will be imputed using a MI model. The MI model will take into consideration the reason and nature of intercurrent event leading to missing data. A detailed plan for constructing and analyzing the primary estimand will be described in the SAP.

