6.5. STATISTICAL TESTS

The default significance level will be 0.05, confidence intervals will be 95%, and all tests will be 2-sided, unless otherwise specified in the description of the analyses.

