
7-day period approach^b
	
DSQ total Score = (Sum of daily DSQ score with 7-day period preceding the scheduled visit day) ×7 / (Number of days with diaries reported with nonmissing* data within 7-day period).
 
Shifting rule when calculating DSQ total score at each visit based on the number of reported diary entries within the 7-day period prior to the visit:
 
Baseline visit and each post baseline visit: If there are less than 4 reported diary entries that are available within the 7-day period prior to the visit, then the most recent 4 reported diary entries in a consecutive 7-day period would be used to calculate the DSQ total score. In order to determine the most recent 7-day period with the minimum number of reported diaries, it may be necessary to make adjustments in some cases by shifting to earlier diary entries. Such 7-day periods cannot be shifted for more than 7 days (not including the study visit day). After shifting 7 days, if there are still less than 4 reported diary entries within the 7-day period, then the DSQ total score for baseline visit will be set to missing.
 
The DSQ total score range is 0 to 42
	
Same as 14-day period approach

^a Primary approach to calculate DSQ total score

^s Sensitivity approach to calculate DSQ total score

Change from Baseline in esophageal PEC at Week 16 will be based on the central EGD results.

Proportion of subjects with esophageal PEC < 15 eos/hpf and ≤ 6 eos/hpf at Week 16, will be based on central reading of the EGD results. Subjects who achieve esophageal PEC < 15 eos/hpf and ≤ 6 eos/hpf will be referred to as responders, respectively. Subjects who do not achieve esophageal PEC < 15 eos/hpf and ≤ 6 eos/hpf will be referred to as nonresponders, respectively.

Planned Analyses by Endpoint

Endpoint (at Week 16)	ANCOVA ^a / Weighted MH	Sensitivity Analyses: MI	Sensitivity Analyses: Tipping Point Analysis	Completer Sets and Per Protocol Set	Linear mixed effects model
Key primary endpoints					
Percent Change from baseline in esophageal PEC	X ^c	X ^e	X ^c	X ^c	
Key secondary endpoints					
Change from baseline in DSQ total score		X ^{e, f}	X ^{e, f}	X ^{e, f}	X ^{b, f, g}
Change from baseline in esophageal PEC	X ^c	X ^e	X ^c	X ^c	
Proportion esophageal PEC < 15 eos/hpf	X ^d	X ^e		X ^d	
Proportion esophageal PEC ≤ 6 eos/hpf	X ^d	X ^e		X ^d	

^a No rank transformation will be applied

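### Absolute change in PEC is analysed by untransformed ANCOVA with one pooled variance and placebo as the smallest arm; if etrasimod shrinks the spread of PEC, the 95% intervals against placebo are too narrow

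*SAP*

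**What the plan says.** Change in PEC at Week 16 is Key Secondary Estimand 2 (SAP 2.4). For its analysis, SAP 17.2.3.1 says: "Change from Baseline in Esophageal PEC at Week 16 will use an ANCOVA model including treatment group and randomization stratification factors as factors". Baseline PEC is the covariate. LS-mean differences, p-values and 95% intervals are reported for 1 mg, 2 mg and pooled etrasimod against placebo. The two dose contrasts come from one three-arm model and the pooled contrast from a two-group model.

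The scale is raw. The protocol synopsis says: "When applying the same ANCOVA model to key secondary continuous variables, no rank transformation will be used". Footnote a of the planned-analyses table in SAP 17.2.1, attached to the ANCOVA column, says: "No rank transformation will be applied". For percent change in PEC, by contrast, Protocol 11.5 uses ANCOVA "based on rank scores due to the skewed distribution of the data and possible outliers".

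On size and allocation, the synopsis says "Approximately 96 subjects are planned to be enrolled" and "Eligible subjects will be randomized in a double-blind fashion (3:3:2 ratio) to etrasimod 1 mg, etrasimod 2 mg, or matching placebo once daily". SAP 6.5 adds: "The default significance level will be 0.05, confidence intervals will be 95%, and all tests will be 2-sided".

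The readable text gives no arm-specific variance, robust standard error, bootstrap, or log- or rank-scale analysis for this endpoint. The readable sensitivity analyses deal with missing data and analysis sets.

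**The concern.** Percent change and absolute change are computed from the same counts. The plan protects the first against skewness and outliers and leaves the second unprotected.

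Ordinary ANCOVA estimates one residual variance from all subjects, and 72 of the 96 are on etrasimod. If treatment lowers PEC roughly in proportion, the spread of the etrasimod counts falls too. The pooled variance is then dominated by the arms with the smaller spread, while the uncertainty of each contrast comes mostly from the small placebo arm with the larger spread. The model standard error is too small and the interval too short.

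A second effect arises if the doses differ. An active 2 mg arm lowers the pooled variance that is also used to compare 1 mg with placebo, so an inert 1 mg dose can look better supported than it is. Choosing a dose is one of the primary objectives (Protocol 2). Protocol 3.3 reports that in the ulcerative colitis study only 2 mg, not 1 mg, differed significantly from placebo. That does not show 1 mg to be inert, but it makes an uneven dose response worth considering.

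**Working it through.** There is no figure of the plan's own to reproduce: the sample-size text is redacted and no SD or effect size for PEC is readable.

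**Inputs from the documents.** N is about 96 at 3:3:2, so 96 × 3/8 = 36 for each etrasimod dose and 96 × 2/8 = 24 for placebo. Intervals are two-sided 95%.

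**Assumed.** r is the residual SD on etrasimod divided by that on placebo, the same for both doses unless stated. Placebo SD is set to 1. Data are complete.

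**Closed form**

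- Pooled variance = (24 + 72r²)/96
- Model SE², one dose = pooled variance × (1/24 + 1/36); any dose = pooled variance × (1/24 + 1/72)
- True SE², one dose = 1/24 + r²/36; any dose = 1/24 + r²/72
- Coverage = 2Φ(1.96 × model SE/true SE) − 1

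Worked case, r = 0.5, one dose: pooled variance = (24 + 18)/96 = 0.4375. Model SE² = 0.4375 × 0.06944 = 0.03038. True SE² = 0.04167 + 0.00694 = 0.04861. The SE ratio is √0.625 = 0.79, and coverage = 2Φ(1.55) − 1 = 87.9%.

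| r | One dose | Any dose |
|---|---|---|
| 1.0 | 95.0% | 95.0% |
| 0.7 | 91.6% | 90.1% |
| 0.5 | 87.9% | 85.0% |
| 0.3 | 83.4% | 79.1% |
| limit 0 | 79.4% | 74.2% |

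**1 mg inert, 2 mg active.** Pooled variance = (60 + 36r²)/96, with r for the 2 mg arm only. The true SE² for 1 mg against placebo is 1/24 + 1/36, so the SE ratio is the square root of the pooled variance. At r = 0.5 this is √0.719 = 0.848: coverage 90.3%, type I error 9.7%. At r = 0.2 it is √0.64 = 0.80: coverage 88.3%, type I error 11.7%.

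**Simulation.** There were 4,000 trials per scenario, 24/36/36, with ANCOVA of raw change on treatment, two binary factors and baseline. Assumed: log-normal counts, baseline at least 15, median about 50, log SD 0.7, log correlation 0.4. Responders fall by 90% and the others are unchanged.

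| Scenario | Planned: 1 mg / 2 mg | Planned: any dose | HC3: 1 mg / 2 mg |
|---|---|---|---|
| No effect | 94.4 / 95.3% | 94.6% | 95.8 / 96.3% |
| Both reduce 30% | 91.8 / 91.8% | 90.5% | 95.0 / 95.3% |
| Both reduce 50% | 87.4 / 87.3% | 84.8% | 93.7 / 93.4% |
| Reduce 50% and 70% | 83.8 / 85.2% | 81.9% | 93.0 / 91.3% |
| Both reduce 80% | 79.2 / 79.1% | 74.2% | 91.7 / 91.8% |
| 30% respond | 95.9 / 95.4% | 95.4% | 96.4 / 95.9% |
| 50% respond | 94.8 / 94.2% | 94.8% | 95.3 / 95.1% |
| 70% respond | 93.4 / 92.8% | 92.7% | 95.3 / 95.2% |
| 1 mg inert, 2 mg reduces 50% | 90.6 / 94.8% | 93.4% | 95.2 / 93.8% |
| 1 mg inert, 2 mg reduces 80% | 89.7 / 94.5% | 95.4% | 96.0 / 92.2% |

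With 32 per arm, the 50%/70% case rises to 89.5/90.6%, so the allocation accounts for a good part of the loss.

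Arm-specific variances with Satterthwaite df, simulated without the two binary factors, gave 91-94% for uniform reductions of 30% to 80%. At 90% responders (Week 16 SD ratio 0.48) that model moved coverage from about 87% to 93%.

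**The case against.** The strongest reply is that the size rests on an assumption the documents do not supply. A reader might infer that whenever etrasimod works these intervals cover only about 80-90%. The plan does not support that. Such figures need the etrasimod spread to fall to well under about two thirds of the placebo spread, as when every subject's count shrinks by a similar factor. If benefit is confined to responders, non-responders keep the spread wide: at 50% and 70% responders the Week 16 SD ratios are 0.91 and 0.76, and coverage is about 95% and 93%. This part of the reply stands, and the claim has to be conditional.

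Other points also stand in part:

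- A reader might take this for the only analysis giving an effect in eos/hpf. Protocol 11.5 also sends longitudinal continuous endpoints, citing the list that contains absolute PEC change, to a linear mixed model. No arm-specific covariance is stated there, so it offers no visible protection, but it is a second analysis.
- SAP 17.2.4 and 17.2.5, on supplementary and sensitivity analyses of secondary variables, appear in the contents but cannot be read. A safeguard there cannot be excluded.
- SAP 17.2.2 carries the primary's missing-data methods, including multiple imputation, over to this endpoint. The figures above are for complete data.
- The trial is Phase 2 with unadjusted p-values. The primary is on ranks, the responder endpoints are unaffected, and no dose-selection rule is tied to this interval.

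None of this removes the mechanism or supplies a reason to keep the equal-variance default.

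**Conclusion.** The concern holds in conditional form. The model, the raw scale, the acknowledged skewness and the small placebo arm are all in the documents. That the variance is pooled is inferred from the default of the model named; the documents do not say it.

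If etrasimod narrows the distribution of PEC, the intervals against placebo are too short. One-dose coverage is 91.6%, 87.9% and 83.4% at SD ratios of 0.7, 0.5 and 0.3, and it is lower for any dose. If the SDs are similar, including when 30-70% of subjects respond, the loss is about two percentage points at most.

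Two opposite inferences about type I error are both wrong. It is not inflated in general, because with both doses inert the test is nominal. It is not always safe either: an inert 1 mg beside an active 2 mg gives about 9-12% at 2 mg SD ratios of about 0.5 or below.

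This should be fixed. It concerns one secondary endpoint and gives no ground for doubting the primary analysis.

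**What to change.** In SAP 17.2.3.1, keep absolute change as the endpoint and the LS-mean difference as the estimate. State that residual variances are arm-specific (PROC MIXED with REPEATED / GROUP=treatment), or that HC3 standard errors are used, with Satterthwaite-type degrees of freedom. Use the same choice for p-value and interval, in both the three-arm and the any-dose model, and apply it within each imputed dataset before pooling by Rubin's rules.

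Optionally add a log- or rank-scale sensitivity analysis of this same endpoint. Do not take the p-value from the rank ANCOVA of percent change: that tests a different endpoint and could disagree with the interval reported beside it.

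The cost is one sentence and one programming option. Intervals become somewhat wider when variances differ and change little when they do not. Coverage improves to about 89-95% rather than exactly 95%, because skewness with 24 placebo subjects remains. The lower end comes from reductions of 60% and 80% with HC3 and ordinary residual degrees of freedom. The choice should be fixed before the unblinding for the Main Analysis, since a variance model chosen afterwards would look data-driven.
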